Mismatch negativity (MMN) as a measure of target engagement: The present project utilizes MMN as both a neurophysiological proxy of plasticity and a measure of NMDAR target engagement. MMN^{66,67} is a neurophysiological response (ERP) elicited most commonly in the context of an auditory oddball paradigm. In this paradigm, a sequence of repetitive standards is interrupted infrequently by a physically different oddball stimulus. Deviants may differ from standards in one or more physical and/or abstract dimensions, including frequency, intensity or duration^{68,69}. Deficits in auditory MMN generation in Sz were first demonstrated in the early 1990’s and have been replicated extensively since then^{7,70-76}. In addition, test-retest reliability of MMN is high, showing an ICC of 0.9⁷², encouraging its use as a neurophysiological biomarker for new treatment development^{32,77}. Deficits in MMN correlate extensively with poor premorbid function and impaired psychosocial outcome even following covariation for more general demographic and neurocognitive factors^{35,37,70,76,78-80}.

In addition to assessing plasticity, MMN has been linked to NMDAR dysfunction across rodent^{147,148}, monkey^{77,149} and human¹⁵⁰⁻¹⁵⁵ investigations, and confirmed in a recent meta-analysis¹⁵⁵. MMN is tied to NMDAR function at the level of auditory sensory cortex¹⁵⁶⁻¹⁶⁰. MMN has also been linked to glutamatergic functioning by recent studies^{161,162} showing that MMN deficits predict parallel deficits in proton magnetic resonance spectroscopy (¹H MRS) measured glutamate. By contrast, MMN is unaffected by treatment with antipsychotics^{76,163,164}, suggesting relative specificity for glutamatergic vs. dopaminergic mechanisms.

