Dose-dependent improvements in target engagement, clinical symptoms and cognition were seen. A dose response for target engagement was supported by a large effect size improvement in MMN during high dose D-serine treatment vs. placebo ($p=0.001$, $d=1.7$), consistent with our double-blind study ($d=2.3$). By contrast, the 30 mg/kg dose was not individually significant vs. placebo ($F_p=0.23$, $d=0.7$). Definitive analysis of the individual doses was limited by a small sample. While all doses produced significant improvement on the PANSS total (all $p<0.05$), only the 120 mg/kg produced specific, significant improvement on PANSS negative symptoms. Similarly, large effect size treatment effects were observed for the MCCB at both the 60 ($p<0.001$; $d=1.1$) and 120 ($p=0.01$; $d=0.99$) mg/kg doses, but not at 30 mg/kg ($p=0.39$; $d=0.25$). A significant dose effect was supported by significantly greater improvement at ≥ 60 mg/kg vs. 30 mg/kg dose for the MCCB composite ($p=0.017$), with specific improvement in auditory cognition (Verbal Memory Domain, $p=0.035$). Finally, pharmacodynamic analysis also supports a dose effect, as increasing peak serum levels predicted MCCB improvements ($r_s=0.38$, $p<0.01$).

The present project will be the first to assess plasticity and target engagement of weekly treatment of D-serine in doses >60 mg/kg.

See main grant for references

Specific Aims and Hypotheses

Concisely state the objectives of the study and the hypothesis or primary research question(s) being examined. There should be one hypothesis for every major study procedure or intervention. For pilot studies, it is important not to overstate the study's objectives. If there are no study hypotheses, describe broad study goals/aims.

Aim #1 (R61): To determine target engagement and safety of D-serine enhancement of auditory plasticity. 45 Sz patients will be randomized to receive three auditory remediation sessions + a double-blind dose of D-serine (80, 100 or 120 mg/kg) vs. placebo. *Hypothesis: Based on our pilot data, we hypothesize that D-serine will be safe and lead to greater plasticity, MMN and θ -ITC changes than placebo, with the largest effect at 120 mg/kg.*

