5. Medically stable for study participation	Medical history, physical examination and screening laboratory parameters, information from clinical team, review of medical record.
6. Taking an antipsychotic medication other than clozapine at a stable dose for at least 4 weeks	Self report
7. Judged clinically not to be at significant suicide or violence risk.	The Columbia Suicide Severity Rating Scale (C-SSRS); clinical interview
8. Clinically stable for 2 months (CGI \leq 4)	Screening CGI
9. Moderate or lower cognitive disorganization (PANSS P2 \leq 4)	Screening PANSS
10. Visual acuity corrected to at least 20/30	Screening exam
11. An estimated Glomerular Filtration Rate (GFR) \geq 60	Screening labs
12. Fluent English speaker	Screening exam
13. Normal conversational hearing	Screening exam
14. Willing to use qualified methods of contraception for the study duration and up to 2 months after its end	Screening exam

CRITERION	METHOD OF ASCERTAINMENT
Exclusion:	
1. Substance abuse (excluding nicotine) within last 60 days	Physician evaluation/SCID
2. ECG abnormality that is clinically significant in the context of study participation in the opinion of the study cardiologist	ECG
3. Current clozapine use. Clozapine is excluded for two reasons: to avoid the potential confound of treatment resistant patients and because of clozapine's intrinsic NMDA agonist	Self report.

4. Participation in study of investigational medication/device within 4 weeks	Self report
5. Pregnant women or women of child-bearing potential, who are either not surgically-sterile or for outpatients, using appropriate methods of birth control. Women of child-bearing potential must have a negative serum β -hCG pregnancy test at screening.	Instructions to study subject, pregnancy tests as per protocol and review of the medical record.
6. Presence of positive history of unstable significant medical or neurological illness	Medical history and screening labs
7. Positive toxicology screen for any substances of abuse	Urine toxicology screen. Positive tests may be repeated at the discretion of the study investigator for suspected false positive
8. Subjects with suicidal ideation with intent or plan (indicated by affirmative answers to items 4 or 5 of the Suicidal Ideation section of the baseline C-SSRS) in the 6 months prior to screening or subjects who represent a significant risk of suicide in the opinion of the investigator	Screening C-SSRS

Study Procedures

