Permitted medications: Subjects will be receiving antipsychotics at doses within the PORT criteria (Lehman, Kreyenbuhl et al. 2004) whenever possible. Patients will be allowed to receive the following adjunctive medications during the course of the study: anticholinergic agents; beta-blockers; mood stabilizers, antidepressants; and anti-anxiety agents. PRN doses of clinically determined benzodiazepines or antipsychotics will be permitted. Given a possible detrimental effect on cognition, patients will be asked to not take these medications the night before or on the day of testing/training session if clinically feasible. The clinical decision will largely be based on a discussion with the subject. The study doctor will ask the subject about their use of PRN benzodiazepines or antipsychotics. For example, if the subject reports that they tend to sleep poorly or have excessive anxiety without them, then they will be permitted. We will err on the side of allowing PRN's. These procedures have been successfully used in our prior published D-serine studies with good effect.

Safety: The primary concern during D-serine treatment is potential for nephrotoxicity. Safety procedures, will be similar to prior D-serine studies (see criteria for early discontinuation). While primary safety focus is on renal function (serum creatinine, BUN, microscopic urinalysis), other measures obtained are liver function tests, CBC, fasting glucose, and general chemistry.

Plasma D-serine levels: Venous blood samples (10 mL per blood draw) will be drawn after the auditory remediation session for assay at the Analytical Psychopharmacology laboratory.

A full description of outcomes is found in section 4.3 of the main grant.

Milestones and Rationale (Go/No-Go Criteria):

Per the R61-R33 mechanism, we are required to meet predesignated milestones prior proceed to the R33. These include target engagement criteria of specific improvement in plasticity, MMN amplitude and θ -ITC, a relationship between plasticity and MMN and safety. Full detail is found in the main application, section 3C4 (page 111).

End of Participation

Care at termination of the study will transfer back to their previous providers and if subjects are hurt by the study their medical care will be provided, but their insurance will be billed for the care. Any relevant health information revealed during the study will be shared with the subject or their health care provider at the subject's request.

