Dose escalation plan: *This study has a built-in space between doses, maximizing safety. Furthermore, no side effects were noted in our prior, once weekly intermittent treatment study.* For the present study, potential nephrotoxicity will be monitored through serum chemistry and urine microscopic examination looking for evidence of active sediment (e.g. casts), proteinuria or glycosuria after each dose, as per FDA suggestions. No subjects with baseline renal impairment, as evidenced by a GFR<60 or clinically abnormal laboratories will be enrolled in the study. As attached, FDA has approved our IND, which incorporates the monitoring procedures described above as well as a sequential dose escalation to identify the maximum tolerated dose.

Placebo

The primary risk with placebo is that patients' symptoms may get worse or may not improve. Since patients will remain on their antipsychotic, and the risk of placebo is small.

Potential subjects will be informed about the results of previous studies and will be encouraged to seek treatment outside of the study as an alternative to study participation if they wish.

Antipsychotics:

All subjects will be asked to remain on their pre-study antipsychotics during the study, and any dose changes for this 6 week study, if any, will be included as co-variables for analysis

EEG Recordings

These studies entail the recording of EEG from the scalp employing standard sensors and amplification methods. These procedures are well standardized and there are few known risks. These are principally due to equipment malfunction. The recording equipment used in these studies meet the current design criteria for subject safety, including isolation from potential electrical hazards. Regular preventative maintenance and careful attention to recording procedures further minimize the already insignificant risks of electrophysiological recording. Electrodes and materials used for affixing them in place are kept scrupulously clean and sterilized and materials are utilized which minimize the chance of skin and scalp irritation. Urine pregnancy tests will be conducted at the time of EEG on all female patients to confirm that the patient is not pregnant prior to study drug administration.

Interviews and Neuropsychological Assessments

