## **Statistical Analysis Plan & Power**

Before any specific statistical techniques are applied, we will examine all variables at all time points for illegitimate values, outliers, and other inconsistencies. Distributions of demographic variables and other clinically important baseline variables will be examined and summarized by means, standard deviations, minima, and maxima for continuous measures and proportions for categorical measures. We will make every effort to obtain all data to reduce or eliminate missing data issues. Intent-to-treat analysis will be implemented for all estimation and testing. Tests will be two-sided and statistical significance determined by  $p < 0.05$ .

**R61 Component.** Summaries of clinical and demographic variables will be provided for each of the three cohorts (C1) D-serine 80mg/kg (n = 12) vs. placebo (n = 3), (C2) D-serine 100mg/kg (n = 12) vs. placebo (n = 3), and (C3) D-serine 120mg/kg (n = 12) vs. placebo (n = 3). As a precaution, any indication of imbalance on important baseline measures between treatment arms (despite randomization) will trigger investigation of whether differences in the primary outcome measures are attributable to these imbalances. For analyses described below, the placebo groups from each of the three cohorts will be combined to yield an effective placebo group of n = 9, unless descriptive analyses suggest systematic differences between the three placebo groups, in which case the groups will remain separate in subsequent analyses.

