Aim 1 Analysis: Aim 1 hypothesizes that D-serine will lead to greater plasticity, MMN, and theta-ITC changes than placebo, with the largest effect being seen at the 120mg/kg dose. Plasticity improvement (defined as change from trials 20 – 30 to trials 70 – 80 at end of session) in the 3rd week of treatment will be examined by using Cohen's d effect size estimates. Within each D-serine group, Cohen's d for within-subject change will be computed by taking the mean change in plasticity divided by the pre-treatment standard deviation. Similar Cohen's d values will be computed for the combined placebo group. Corresponding 95% confidence intervals (based on standard theory or constructed via bootstrapping if assumptions for constructing the confidence intervals based on parametric methods are not satisfied) will be computed. Similar procedures will be followed for assessing within-subject changes in MMN and theta-ITC. For each D-serine dose level, Cohen's d for between-group differences will be computed as (mean change for the D-serine group minus mean change for the placebo group) divided by standard deviation of the change scores in the combined placebo group.

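### Adjusting for antipsychotic dose changes made after randomisation can bias the D-serine versus placebo comparison, and conflicts with the SAP's intent-to-treat, unadjusted estimate

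*Protocol*

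**What the plan says.** The protocol's Antipsychotics paragraph, under Risks/Discomforts/Inconveniences, opens with "All subjects will be asked to remain on their pre-study antipsychotics during the study" and goes on: "any dose changes for this 6 week study, if any, will be included as co-variables for analysis". The wording is mandatory. It does not say which outcome, model or comparison is meant, or how a change is coded.

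The SAP text seen for this point does not carry the rule. Its opening paragraph states "Intent-to-treat analysis will be implemented for all estimation and testing". Its R61 Component paragraph provides only for looking into imbalance on baseline measures. Its Aim 1 Analysis defines the group contrast without a covariate: "Cohen's d for between-group differences will be computed as (mean change for the D-serine group minus mean change for the placebo group"), divided by the standard deviation of change in the combined placebo group.

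Other protocol statements bear on how often dose changes might occur and whether they matter:
- Inclusion criterion 6: "Taking an antipsychotic medication other than clozapine at a stable dose for at least 4 weeks".
- Study Procedures, Permitted medications: "PRN doses of clinically determined benzodiazepines or antipsychotics will be permitted".
- Background, Dose Finding, on earlier D-serine data: "While all doses produced significant improvement on the PANSS total".
- Background, on mismatch negativity: "MMN is unaffected by treatment with antipsychotics".

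**The concern.** Randomisation makes the arms comparable on everything fixed before it. An antipsychotic dose change afterwards does not have that protection. It may respond to worsening symptoms, and D-serine could alter symptoms. If so, adjusting for dose change can do two things. It can remove the part of the drug effect that works through the change. It can also open a path through unmeasured severity, which drives both the change and poorer performance. Either way the adjusted coefficient no longer estimates the effect of assignment, which is what an intent-to-treat analysis sets out to estimate.

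There is a second problem that needs no assumption about rates. An analyst who follows the protocol sentence for the Aim 1 contrast cannot also follow the SAP formula. Two estimates, adjusted and unadjusted, could each claim to be the planned one, and nothing says which governs. This matters because the R61 go/no-go decision depends on reaching at least a moderate effect size for plasticity, MMN and theta-ITC, so even a modest shift in d could be argued over.

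**Working it through.** The documents give no figure on this point, so there is none to reproduce. The arm sizes are consistent: 3 × (12 + 3) = 45 in total, and 3 × 3 = 9 pooled placebo.

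**1. Can the covariate arise after randomisation?** R61 Design, Table 1 has a baseline window of Day -30 to -1 and treatment on Day 1, Day 8±2 and Day 15±2. Treatment therefore spans about two weeks. A six-week study fits only if the baseline window is counted (30 + 15 = 45 days, about 6.4 weeks). Changes recorded under the rule may fall before or after randomisation, and only the latter cause the problem.

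**2. Size of the shift.** Let p0 and p1 be the proportions with a dose change on placebo and D-serine, and γ the coefficient of dose change in a linear model that also contains treatment. Then

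adjusted − unadjusted difference = γ × (p0 − p1).

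The shift is zero if the rates are equal or if γ = 0.

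**3. Assumed inputs.** None of these comes from the documents:
- p0 from 5% to 33%, and p1 from 5% to 10%.
- Dose change has a latent correlation of 0.5 with an unmeasured severity.
- Severity correlates 0, 0.3 or 0.5 with a poorer outcome.
- A dose change has a direct effect on outcome of 0 or 0.3 SD.
- The direct D-serine effect is 0.5 SD, with 12:9 allocation and 1,000,000 simulated patients per scenario.

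| Placebo vs D-serine rate | Shift from the unadjusted effect (SD) |
|---|---|
| 5% vs 5%, 10% vs 10% | 0.000 |
| 10% vs 5% | −0.025 to +0.015 |
| 20% vs 10% | −0.046 to +0.030 |
| 20% vs 5% | −0.071 to +0.045 |
| 33% vs 8% | −0.109 to +0.076 |

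The identity explains the table. With no severity link and a direct effect of 0.3, γ = 0.3. The last row should then give 0.3 × (0.33 − 0.08) = 0.075, against 0.076 simulated. The negative end of that row implies γ = −0.109 / 0.25 = −0.44, which is the severity path.

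**4. Set against precision.** The approximate standard error of d at 12 versus 9 is √(1/12 + 1/9) = √0.194 = 0.44. The largest shift is 0.109 / 0.44, or about a quarter of one standard error. In patients, that row means about 3 of 9 on placebo (0.33 × 9 = 2.97) and 1 of 12 on D-serine (0.08 × 12 = 0.96). The covariate coefficient would rest on about four people.

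**The case against.** The strongest reply is that the sentence sits in a risk section written for the IRB, names no analysis, and need not govern the Aim 1 estimate at all. That estimate is unadjusted in the SAP. A reader might infer that the primary comparison will be adjusted and is therefore biased. The documents do not support that. They show an unassigned rule that conflicts with the SAP formula.

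The design also makes dose changes unlikely to be many. Patients enter on a stable dose and clinically stable for two months, are asked to stay on their drug, and receive three weekly doses. The evidence that D-serine improves symptoms comes from 4 to 6 weeks of daily dosing. The protocol puts weekly exposure at one seventh of that and reports no side effects in its earlier weekly study. A differential rate by arm is therefore possible but not shown. All of this stands and limits the expected size. It does not make a variable arising after randomisation a suitable covariate.

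Two stronger readings should be resisted:
- **Large bias.** If dose change is treated as fully determined by worsening, an effect of 0.50 can fall to 0.24 after adjustment, and a null effect can appear as +0.33. The first needs a direct D-serine effect of 0.50 − 0.8 × 0.7 = −0.06, so more than the whole benefit would have to run through preventing worsening. The second needs dose changes in about 48% of D-serine patients against 20% on placebo (20% threshold 0.84, shifted by 0.80, leaves the upper tail beyond 0.04). When dose change is only correlated 0.5 with worsening, the 0.24 becomes about 0.43.
- **Worse harm in R33.** More time would allow more changes, but the sentence refers to a six-week study, and the protocol leaves the full R33 description to a later amendment.

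**Conclusion.** The point holds in a limited form. The protocol states a covariate rule that, if applied to a D-serine versus placebo comparison, conditions on a variable arising after randomisation. It conflicts with the intent-to-treat statement and with the covariate-free between-group d. The resulting estimate can be biased; the documents do not establish that it will be.

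In R61 the effect is probably small: none with equal change rates, and up to about 0.1 SD in either direction over the assumed range, against a standard error of about 0.44. That size rests on assumed rates and correlations. The conflict between the documents does not.

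The adjustment also has little to offer. For MMN, the protocol's own view is that antipsychotics have no effect on it.

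One limit applies: the SAP text seen ends at the Aim 1 between-group formula, so covariate use in any later section, including R33, was not checked.

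**What to change.** Replace the covariate sentence in the protocol's Antipsychotics paragraph, and put the same wording in the SAP:

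> Between-group comparisons use outcomes regardless of antipsychotic dose changes after randomisation and are not adjusted for them. Any covariate adjustment uses baseline values only, including antipsychotic dose before randomisation. Dose changes are tabulated by arm, and any analysis that adjusts for or excludes patients with changes is labelled supplementary.

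The supplementary label should also cover an analysis restricted to patients without a change, because that restriction selects on an event after randomisation too. State as well whether PRN antipsychotic use counts as a dose change in the table.

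The cost is one short passage in each document. Antipsychotic treatment before entry is already ascertained for eligibility, and clinical management is unaffected. The downside is that variance due to dose changes is not modelled, which is minor over about two weeks of treatment.

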## **Statistical Analysis Plan & Power**

Before any specific statistical techniques are applied, we will examine all variables at all time points for illegitimate values, outliers, and other inconsistencies. Distributions of demographic variables and other clinically important baseline variables will be examined and summarized by means, standard deviations, minima, and maxima for continuous measures and proportions for categorical measures. We will make every effort to obtain all data to reduce or eliminate missing data issues. Intent-to-treat analysis will be implemented for all estimation and testing. Tests will be two-sided and statistical significance determined by  $p < 0.05$ .

**R61 Component.** Summaries of clinical and demographic variables will be provided for each of the three cohorts (C1) D-serine 80mg/kg (n = 12) vs. placebo (n = 3), (C2) D-serine 100mg/kg (n = 12) vs. placebo (n = 3), and (C3) D-serine 120mg/kg (n = 12) vs. placebo (n = 3). As a precaution, any indication of imbalance on important baseline measures between treatment arms (despite randomization) will trigger investigation of whether differences in the primary outcome measures are attributable to these imbalances. For analyses described below, the placebo groups from each of the three cohorts will be combined to yield an effective placebo group of n = 9, unless descriptive analyses suggest systematic differences between the three placebo groups, in which case the groups will remain separate in subsequent analyses.

Aim 1 Analysis: Aim 1 hypothesizes that D-serine will lead to greater plasticity, MMN, and theta-ITC changes than placebo, with the largest effect being seen at the 120mg/kg dose. Plasticity improvement (defined as change from trials 20 – 30 to trials 70 – 80 at end of session) in the 3rd week of treatment will be examined by using Cohen's d effect size estimates. Within each D-serine group, Cohen's d for within-subject change will be computed by taking the mean change in plasticity divided by the pre-treatment standard deviation. Similar Cohen's d values will be computed for the combined placebo group. Corresponding 95% confidence intervals (based on standard theory or constructed via bootstrapping if assumptions for constructing the confidence intervals based on parametric methods are not satisfied) will be computed. Similar procedures will be followed for assessing within-subject changes in MMN and theta-ITC. For each D-serine dose level, Cohen's d for between-group differences will be computed as (mean change for the D-serine group minus mean change for the placebo group) divided by standard deviation of the change scores in the combined placebo group.

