Provide a clear, concise narrative of study procedures with special attention to the subjects' involvement. Detail the overall study timeline and location of study procedures, list all interventions, assessments and interviews, estimate the duration of each procedure, provide dosing schedules, identify study personnel involved in each procedure, and provide credentials for relevant personnel. For complicated study designs, we strongly encourage attaching tables, flow-charts, and study algorithms.

In the R61, we will confirm target engagement of D-serine + auditory remediation, assess relationships of plasticity changes and cognition, safety and assess the optimal dose of D-serine treatment. In the R33, we conduct a randomized, placebo-controlled, parallel group study with the superior dose of D-serine combined with 16 weekly sessions of the same neuroplasticity-based auditory remediation. The structure of this grant requires successful completion of the R61 phase over 2 years prior to initiation of the R33 phase. We will amend the PSF and consent to include a full description of the R33 phase prior to its initiation.

The study will be conducted in groups of 15 subjects in which 12 subjects will receive D-serine for each of the three treatment visits and 3 will receive placebo for each of the three treatment visits. The first group of 15, will receive 80 mg/kg or placebo, and the second group of 15 subjects will receive 100 mg/kg or placebo, followed by a third group receiving 120 mg/kg or placebo. As previous studies noted minimal carry over effect of D-serine effects ([name] 2010), subjects may be permitted to participate in more than one phase with at least a six

month space in between.

If there are tolerability concerns at the 80 or 100 mg/kg doses, we will add a 60 mg/kg arm, ensuring the assessment of multiple doses. After each cohort, we will obtain permission from both the FDA and the IRB via an amendment, prior to the beginning of the next cohort. We require this safety milestone to be reached in order to begin the next cohort.

R61 Design (Table 1):

R61 Design	Table 1 (R61)	Baseline	Treatment Day			Follow-up ¹
			1	2	3	
		Day -30 to -1	Day 1	Day 8±2	Day 15±2	
	Consent	x				
	Medical screening	x				
	D-serine/Placebo		x	x	x	
	MMN		x	x	x	
	Auditory Remediation/EEG		x	x	x	
	Cognitive and behavioral ratings	x				
	Clinical laboratory/pregnancy/vitals	x	x	x	x	x
	SAFTEE/C-SSRS	x	x	x	x	x
	1. If necessary to follow-up any abnormalities.					

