Screening/Informed consent: Informed consent will be obtained before any study procedures, including screening procedures, are initiated. After providing informed consent, subjects will undergo full medical screening (medical history, physical examination, vital signs, laboratories for basic chemistries, blood counts, liver function tests, urinalysis, urine toxicology, serum pregnancy test for women, and thyroid tests, electrocardiogram [EKG]) and psychiatric screening (i.e., Structured Clinical Interview for DSM V Axis I Disorders (SCID) to confirm eligibility. Screening will occur over an up to 31-day screening period.

Baseline ratings: Eligible subjects will then undergo baseline cognitive and behavioral tests:

Randomization: Assignment to treatment groups will be on a random basis. Randomization will be stratified by baseline tone matching.

Auditory remediation visits: Subjects will then undergo three auditory remediation/EEG sessions. Each visit will follow the same format. Sessions are administered once a week±2 days. We utilize an auditory remediation program, in which participants are presented with paired tones (e.g. Stimulus 1 (“reference”) and Stimulus 2 (“test”): S1 and S2) and indicate which tone is higher in pitch (frequency). In the first pair, the ratio is 50% (e.g. 1000±500 Hz), and the difficulty level is adjusted to maintain a steady (~70% correct) level of performance across the 80 repeats. Ratios in each pair are log-transformed and averaged across 10-trial pairs (e.g., pairs 1-10, 11-20, etc.). When the reference (S1) remains constant (“fixed”), highly significant improvement is seen.

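### By default, six of the nine placebo controls for each dose come from other sequential cohorts, and the supplied SAP text gives no cohort-stratified D-serine versus placebo estimate

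*SAP*

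**What the plan says.** The Protocol describes the R61 allocation in two ways. Aim #1 (Specific Aims and Hypotheses) has 45 patients "randomized to receive three auditory remediation sessions + a double-blind dose of D-serine (80, 100 or 120 mg/kg) vs. placebo", which reads as randomisation among doses. Study Procedures describes sequential cohorts: "The first group of 15, will receive 80 mg/kg or placebo, and the second group of 15 subjects will receive 100 mg/kg or placebo", then a third group at 120 mg/kg or placebo. In each group of 15, "12 subjects will receive D-serine for each of the three treatment visits and 3 will receive placebo". The cohorts cannot overlap, because "we will obtain permission from both the FDA and the IRB via an amendment, prior to the beginning of the next cohort". On the method of assignment, the Protocol adds that "Randomization will be stratified by baseline tone matching".

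In the SAP (Statistical Analysis Plan & Power, R61 Component), the default is that "the placebo groups from each of the three cohorts will be combined to yield an effective placebo group of n = 9", with the exception "unless descriptive analyses suggest systematic differences between the three placebo groups, in which case the groups will remain separate in subsequent analyses". Under Aim 1 Analysis, the only between-group estimate in the supplied text is dose-specific: "For each D-serine dose level, Cohen's d for between-group differences will be computed as" the difference in mean change from placebo, divided by the combined placebo group's change-score SD. No cohort term appears, and no contrast of all D-serine patients with placebo. Yet the Aim 1 hypothesis has two halves: D-serine exceeds placebo, and the effect is largest at 120 mg/kg.

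**The concern.** Dose is fixed by calendar order. What is randomised is D-serine against placebo inside a cohort. With pooled controls, each dose is judged partly against patients studied at another time, so any change over time in how much patients improve enters the dose-specific effect size. An upward drift lowers the 80 mg/kg value and raises the 120 mg/kg value, which is the pattern Aim 1 predicts. Aim #3 makes the R33 dose depend on R61 results, so a false gradient would have consequences.

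Meanwhile, the broader question of whether D-serine beats placebo could be answered using only patients compared with their own cohort's placebo group. The supplied text leaves it to three separate contrasts, each partly non-randomised.

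**Working it through.** **Inputs.** From the Protocol (Study Procedures): three cohorts, 12 D-serine and 3 placebo in each. From the SAP: pooled placebo n = 9. Assumed: equal change-score SD in all groups, no dropout, independent patients, and a linear drift of δ SD per cohort that affects both arms alike.

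**Reproducing the plan's count.** 3 × 3 = 9 placebo, 3 × 12 = 36 D-serine, 36 + 9 = 45 in total. Controls from other cohorts in each default dose comparison: 9 - 3 = 6, or 6/9 = 67%. The supplied SAP text states no R61 power figure to reproduce.

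**Precision.** SE in change-score SD units is √(1/n₁ + 1/n₀).

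| Contrast | Formula | SE |
|---|---|---|
| One dose v pooled placebo (default) | √(1/12 + 1/9) | 0.441 |
| One dose v own-cohort placebo (exception) | √(1/12 + 1/3) | 0.645 |
| All D-serine v placebo, stratified by cohort | √(3 × (1/12 + 1/3))/3 | 0.373 |

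The stratified SE equals √(1/36 + 1/9) = 0.373, because the 12:3 split is the same in every cohort. Fitting cohort therefore costs only two degrees of freedom. With 45 - 4 = 41 df, the 95% half-width is about 0.75 SD.

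**Bias from drift.** Let the cohort shifts in mean change be 0, δ and 2δ. The pooled placebo mean then shifts by (0 + δ + 2δ)/3 = δ.

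- 80 mg/kg: 0 - δ = -δ
- 100 mg/kg: δ - δ = 0
- 120 mg/kg: 2δ - δ = +δ
- 120 minus 80: +δ - (-δ) = 2δ
- Stratified D-serine v placebo: the shift cancels within each cohort, so 0

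**How well the exception could detect drift.** Take a formal F test on three placebo groups of 3 (2 and 6 df, 5% level), with noncentrality 3 × (δ² + 0 + δ²) = 6δ². The SAP specifies only a descriptive look, so this test is a benchmark.

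| δ (SD per cohort) | 6δ² | Power |
|---|---|---|
| 0.2 | 0.24 | 6% |
| 0.3 | 0.54 | 8% |
| 0.5 | 1.50 | 13% |

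**Whether pooling is a poor choice for a single dose.** For 80 or 120 mg/kg, the RMSE with pooled controls is √(0.1944 + δ²), where 0.1944 = 1/12 + 1/9. With own-cohort controls it is 0.645.

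| δ (SD per cohort) | Pooled RMSE | Own-cohort RMSE |
|---|---|---|
| 0.1 | 0.452 | 0.645 |
| 0.2 | 0.484 | 0.645 |
| 0.3 | 0.533 | 0.645 |
| 0.5 | 0.667 | 0.645 |

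The two are equal at δ = √(0.4167 - 0.1944) = 0.47, where 0.4167 = 1/12 + 1/3.

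**The case against.** The case for the plan is substantial, and several stronger readings fail.

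- **Pooling is conditional.** A reader who stops at the n = 9 might infer unconditional pooling. The SAP goes on to make an exception, so its authors saw the risk. That stands. The exception still lacks a criterion, rarely detects drift with three per group, and does not lead to a combined stratified estimate.
- **Pooling is defensible for dose-specific values.** Below about 0.47 SD of drift per cohort it has the smaller RMSE. This stands, and pooling should stay.
- **The stratified contrast is not the only randomised one.** Each 12 versus 3 comparison is randomised too; the stratified estimate combines the three. Nor is 0.373 against 0.441 a like-for-like gain, since the first is for an average over doses and the second for one dose.
- **Drift is assumed.** The documents give no drift size or cohort dates. The COVID-19 procedures show that conditions can change, but not that they changed between cohorts. The outcomes are changes, and plasticity is a within-session change, so stable shifts in level largely cancel. Only drift in the change itself matters.
- **Chance findings are a separate matter.** A reader might point out that, with an inert drug and known SD, at least one of three dose contrasts reaches d = 0.5 about 26% of the time, against 9.0% for the single overall contrast. One dose contrast alone does so 12.8% of the time, so most of that gap comes from three looks instead of one. It is not evidence of harm from non-concurrent controls, and no supplied text sets such a rule.
- **Absence is shown only for the supplied text.** The supplied SAP ends within Aim 1 Analysis, and the Protocol refers the full go/no-go detail to the main application. An overall contrast may exist there.

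**Conclusion.** The point holds as a cheap improvement. By default, 6 of 9 controls for each dose are non-concurrent and were not randomised against that dose. The supplied SAP text also omits the estimate that answers the first half of Aim 1 from randomised comparisons alone.

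The size of any bias is unknown. It would be -δ, 0 and +δ for the three doses under an assumed linear drift, for example ±0.2 SD at δ = 0.2. The stratified estimate is free of drift shared by both arms, with SE 0.373 SD given equal SDs, full follow-up and independent patients. The Protocol's allowance for taking part in more than one phase could break that independence.

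A reader might infer that the stratified estimate would rescue the dose-response reading. It would not: dose remains confounded with calendar order, and an average over doses carries no information on the gradient.

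**What to change.** 1. In the SAP, Aim 1 Analysis, add for each endpoint (plasticity, MMN, theta-ITC) a D-serine minus placebo estimate stratified by cohort: change regressed on treatment and cohort, all 45 patients, with a 95% CI. Report it alongside the dose-specific effect sizes.
2. Keep pooled controls for the dose-specific values, label them as partly non-concurrent, and state that the choice is a bias-variance trade-off.
3. Describe any dose gradient as a non-randomised comparison that the added estimate does not correct.
4. In Protocol Aim #1, align the wording with Study Procedures: randomised to D-serine or placebo within sequential dose cohorts.

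The cost is SAP and protocol wording plus one model per endpoint, with no new patients, visits or measurements. The downside is that the overall estimate averages three doses and is diluted if only one works, which is why the dose-specific values stay.
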